3.5.1. Initiation of Local Standard Treatment for hATTR Amyloidosis

In the APOLLO study, there were placebo-treated patients who discontinued study drug, but remained on study and received local standard treatment. For the primary analysis of mNIS+7 and Norfolk QoL-DN, assessments were censored (excluded from analysis) after initiation of any of the following:

- Orthotopic liver transplant
- Use of TTR stabilizing agents (eg, tafamidis, diflunisal) for >14 days

For consistency of data handling, the placebo group from the APOLLO study will follow the same censoring rule as the APOLLO study.

For this study, APOLLO censoring rules will be applied. Additionally, assessments will be censored after initiation of any of the following recently approved treatments:

- Any use of TTR-targeting anti-sense oligonucleotides (eg, inotersen)
- Any use of patisiran (applicable for the vutrisiran treatment group only)

This data will be included and flagged in efficacy listings. These assessments from either study will be included in sensitivity analyses as specified.

For TTR percent reduction, TTR assessments collected after initiation of local standard treatment for hATTR amyloidosis will be excluded from the analysis. For all other efficacy endpoints, data

from either study collected after initiation of local standard treatment for hATTR amyloidosis will be included in analyses.

A separate listing will be provided for patients who initiate local standard treatment for hATTR amyloidosis while on study.

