4.4.2.3. Sensitivity Analysis: Pattern-Mixture Model

The primary analysis [ANCOVA/MI](#) method addresses data under missing at random (MAR) assumptions. To assess the robustness of the primary analysis results under missing not at random (MNAR) assumptions, a sensitivity analysis using a pattern-mixture model (PMM) will be conducted at Months 9 and 18 using a modified [ANCOVA/MI](#) method.

The model will be based on the following assumptions:

1. Patients who have missing data due to COVID-19, including patients who have missing assessments, who have data censored because a serious COVID-19 AE was reported before Month 9 (or 18), or who die due to COVID-19:
 - a. Under the hypothetical estimand of interest where the COVID-19 pandemic did not occur, these assessments should have been obtained with no COVID-19 impact. Therefore, for patients meeting either of these criteria, assessments will be considered MAR, and will be imputed using MI estimated from all nonmissing data collected on treatment from the vutrisiran group.
2. Patients who have missing data unrelated to COVID-19 and are alive before Month 9 (or 18):
 - a. Placebo-treated patients who have missing data: The missing data are considered MAR and will be imputed using MI estimated from placebo-treated patients. The

- imputation is done regardless of whether a patient was on-treatment or discontinued treatment before the scheduled Month 9 (or 18) efficacy assessment.
- b. Vutrisiran-treated patients who have missing data while on treatment: Patients are expected to continue to show benefit from treatment similar to that observed at the scheduled time point. Therefore, missing data during the on-treatment period (within 126 days of the patient's last dose before the scheduled Month 9 [or 18] efficacy assessment) are considered MAR and will be imputed using MI estimated from all nonmissing data collected on treatment from the vutrisiran group. The 126-day window was selected given the long PD effect of vutrisiran.
 - c. Vutrisiran-treated patients who have missing data after stopping their study treatment: Patients will no longer benefit from treatment in the future and will have trajectory similar to placebo-treated patients. Therefore, missing data after treatment discontinuation (more than 126 days after the patient's last dose of study drug before the scheduled Month 9 (or 18) efficacy assessment) will be imputed using the data from placebo-treated patients.

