4.5. Pharmacodynamic Analyses

The PD parameters include serum TTR and vitamin A. All summary tables and figures will be based on assessments within 21 days after last dose of patisiran or within 84 days after last dose of vutrisiran. Assessments more than 21 days after last dose of patisiran or more than 84 days after last dose of vutrisiran will be presented in listings and individual patient plots only.

Summary tables will be provided for observed values, changes and percentage changes from baseline for each scheduled time point by treatment group for TTR and vitamin A during the study (also see details in Section [6.1](#)).

In addition to TTR percent reduction analyses specified in Section [4.4.3.3](#), the following parameters, derived using all available TTR samples within the specified windows (including nontrough and unscheduled), will be summarized using descriptive statistics:

- Maximum percentage reduction in serum TTR and vitamin A over 9 and 18 months
- Mean percentage reduction in serum TTR and vitamin A over 9 and 18 months
- Mean percentage reduction in serum TTR at steady-state from Month 6 to 9 and from Month 6 to 18

Subgroup analysis for maximum and mean percentage reduction in serum TTR described above will be provided for the following subgroups:

- Age (years) [≥ 65 ; < 65]
- Sex [Male; Female]
- Race [White; All other races]
- Previous tetramer stabilizer use [Yes; No]

- Genotype [V30M; non-V30M]
- Weight (kg) [<65 ; ≥ 65]

Summary of TTR levels over time for patients in the patisiran group before and after the switch to vutrisiran will be presented to evaluate maintenance of serum TTR levels following switch from patisiran to vutrisiran.

All PD data will be displayed in data listings.

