9.2. Pattern-Mixture Model Details

Similar to the primary analysis methods, assessments after initiation of local standard treatment will be treated as missing and thus imputed following the PMM procedure.

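### The pattern-mixture analysis applies no MNAR departure to vutrisiran patients who start another hATTR treatment when their last dose is within 126 days of the scheduled visit

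*SAP*

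**What the plan says.** References are to SAP Amendment 3.

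- **Censoring (3.5.1).** For mNIS+7 and Norfolk QoL-DN, assessments in the vutrisiran arm are excluded after liver transplant, a TTR stabiliser for more than 14 days, any antisense drug, or patisiran: "Any use of patisiran (applicable for the vutrisiran treatment group only").
- **Entry into the PMM (9.2).** "assessments after initiation of local standard treatment will be treated as missing and thus imputed following the PMM procedure".
- **Rule 2b (4.4.2.3).** Missing data "within 126 days of the patient's last dose before the scheduled Month 9 [or 18] efficacy assessment) are considered MAR" and are imputed from on-treatment vutrisiran data. The reason given is "Patients are expected to continue to show benefit from treatment similar to that observed at the scheduled time point", and the window is justified by vutrisiran's long pharmacodynamic effect.
- **Rule 2c (4.4.2.3).** This rule is headed as covering data missing once study treatment has stopped. Its rationale is "Patients will no longer benefit from treatment in the future". Data missing "more than 126 days after the patient's last dose of study drug" "will be imputed using the data from placebo-treated patients".
- **Other patterns.** COVID-19-related missingness and non-COVID death each have their own rule. Starting another hATTR treatment has none in the visible text.

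The PMM's stated aim is to test the primary result under missing-not-at-random (MNAR) assumptions. It covers mNIS+7 and, through 4.4.3.1, Norfolk QoL-DN. Amendment 3 extended it to Month 18 to support the EU primary endpoint.

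**The concern.** Starting another hATTR treatment may reflect perceived failure of vutrisiran. If so, missing at random (MAR) is hard to defend for these patients, and they are among those an MNAR check most needs to stress. Under the visible rules, some are instead imputed as if vutrisiran were still working, which is the assumption the primary analysis already makes. For that subgroup, agreement between the PMM and the primary analysis is not evidence of robustness.

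The wording also pulls two ways. A patient who stopped vutrisiran 100 days before the visit and began another therapy fits the heading and rationale of 2c, but the day count puts that patient in 2b.

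**Working it through.** **Plan's own figure.** The related figure in 1.4 is power above 90% for mNIS+7 (placebo mean 15, SD 17; vutrisiran mean 0; two-sided 0.05). The placebo sample size is not given there, so it cannot be reproduced strictly. With 160 × 3/4 = 120 vutrisiran patients, power exceeds 90% for any placebo n of 16 or more. That figure is not in dispute.

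**Step 1: which rule applies.** Dosing is every 12 weeks (1.1; Table 3), so dose day = 1 + 84k: Day 1, Week 12 = Day 85, Week 24 = Day 169, Week 36 = Day 253, Week 48 = Day 337, Week 60 = Day 421, Week 72 = Day 505. The visit days are assumptions, two for each visit:

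- Month 9: Day 253 (Week 36) or Day 274, the midpoint of the days in 9.1.5, (190 + 358)/2.
- Month 18: Day 505 (Week 72, equated with Month 18 in Section 2) or Day 547 (9.1.5).

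Interval = visit day − dose day, compared with 126:

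| Visit | Last dose | Interval, days | Rule |
|---|---|---|---|
| Month 9 | Day 1 | 252 or 273 | 2c, placebo |
| Month 9 | Week 12 | 168 or 189 | 2c, placebo |
| Month 9 | Week 24 | 84 or 105 | 2b, vutrisiran |
| Month 18 | Week 48 | 168 or 210 | 2c, placebo |
| Month 18 | Week 60 | 84 or 126 | 2b, vutrisiran |

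A patient still being dosed when the other treatment starts is also in 2b: a Week 36 dose is 274 − 253 = 21 days before Month 9, and a Week 72 dose is 547 − 505 = 42 days before Month 18.

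The Month 9 assignments are the same under either visit day. The Week 60 case is clear at 84 days but sits exactly on the cut at 126; one day later would move it to 2c.

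**Step 2: comparison with the primary analysis.** Section 4.4.1.1 imputes missing values separately within each treatment group under MAR. Rule 2b also imputes vutrisiran patients from vutrisiran data under MAR. For a patient in 2b, the PMM therefore departs from the primary assumption in no material way.

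**Step 3: size at Month 9.** Let f be the share of vutrisiran patients moved from 2b to placebo-based imputation. The planned gap is 15 − 0 = 15 points, so shift = 15 × f. The SAP gives no rate, so f is an assumption.

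| f | Patients (120 × f) | Shift, points | Planned difference after shift |
|---|---|---|---|
| 2% | 2.4 | 0.3 | 14.7 |
| 5% | 6 | 0.75 | 14.25 |
| 10% | 12 | 1.5 | 13.5 |
| 20% | 24 | 3.0 | 12.0 |

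**Step 4: consequence for the conclusion.** With an assumed placebo n of 40, power is 99.8% at a difference of 15. Widening the SD for the mixture, √(17² + f(1 − f) × 15²), gives 99.5% at f = 5%, 98.8% at 10% and 95.4% at 20%.

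Section 1.4 gives no planning means for Month 18, so no size is computed there.

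**The case against.** **Patients beyond the window are covered.** A reader might infer that every vutrisiran patient who moves to another therapy is imputed as still benefiting, or that the MNAR check misses all of them. The documents do not support that. Rule 2c gives placebo-based imputation whenever the last dose is more than 126 days before the visit, and non-COVID deaths are drawn from the worst 10% of scores. This stands, and it limits the point to patients inside the window.

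**Other analyses look at these patients.** Section 4.4.2.1 keeps the observed scores after local standard treatment at both visits, and 4.4.3.1 extends this to Norfolk. The binary analysis counts non-COVID missing changes as non-response. This also stands, so it would be wrong to say the plan ignores them. But scores observed after the start of a new therapy include that therapy's effect, so 4.4.2.1 answers a different question and is not an MNAR imputation.

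**The implementation is redacted.** Most of 9.2.1 and 9.2.2 is blacked out, and a variable for other treatment there cannot be excluded. That is a real limit. Still, 4.4.2.3 sets out the governing assumptions and none mentions it.

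**The 126-day window has a reason.** A patient dosed through Week 24 may still have TTR suppression, so a full placebo trajectory is not self-evidently more credible. This is fair, and is why reporting both versions is acceptable. A reader might also take the PD summary window in 4.5, "within 84 days after last dose of vutrisiran", as contradicting 126 days. It does not: 84 days is one dosing interval, used for PD summaries and adverse-event attribution, and says nothing about when clinical benefit ends.

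**Conclusion.** The point holds in limited form. Under the visible rules, vutrisiran patients who start another hATTR treatment and whose last dose is no more than 126 days before the scheduled visit are imputed under the same MAR assumption as in the primary analysis. For them the PMM is not an MNAR test, and their placement conflicts with how 2c is headed.

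The likely effect is small: 0.3 to 1.5 mNIS+7 points of a planned 15 at Month 9, if 2% to 10% of vutrisiran patients are affected. This rests on the assumed rate, the planning means in 1.4 and the assumed visit days. It is unlikely to change the trial's conclusion. What changes is how much robustness the PMM can claim to have shown, for the Month 9 endpoints and for the EU primary at Month 18.

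**What to change.** In 4.4.2.3, state that vutrisiran patients whose score is censored or missing because local standard treatment was started are imputed from placebo data (2c) at Months 9 and 18, regardless of days since last dose. Rule 2b then covers only patients who have not started another hATTR treatment. Add a matching flag to the intermediate datasets in 9.2 for mNIS+7 and Norfolk QoL-DN, unless the redacted text already holds one.

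If the sponsor wishes to keep the 126-day rule because of the PD effect, the minimum is to report the placebo-based version as a second PMM run beside it.

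The cost is one clause, one flag and at most one extra run. The downside is a slightly less favourable sensitivity estimate for vutrisiran.

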4.4.2.4. Other Analysis: Binary Endpoint

The number and percentage of patients with a decrease (change from baseline < 0) in total score of mNIS+7 from baseline to Month 9 and to Month 18 will be summarized. The endpoint will be analyzed using Cochran-Mantel-Haenszel (CMH) test with Mantel-Haenszel odds ratios and associated CIs presented, stratified by genotype (V30M vs. non-V30M). Patients with missing change from baseline values due to COVID-19 will be excluded; all other patients with missing change from baseline values will be considered non-responders.

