3.4. Randomization Stratification Factors

Stratification factors for randomization into the 18-Month Treatment Period include TTR genotype (V30M vs. non-V30M) and baseline NIS score (< 50 vs. ≥ 50).

Stratification factors are recorded in both the Interactive Response System (IRS) and the clinical database. In statistical analyses that use randomization stratification factors as covariates, the stratum assignment will reflect the values as recorded in the clinical database. In the presence of stratification errors, the stratification used in analysis may not match that in the IRS.

In addition to the initial randomization, [REDACTED]

[REDACTED] For patients initially randomized to vutrisiran, stratification factors for this 2nd randomization include TTR genotype (V30M vs. non-V30M) and the most recent FAP stage (0/1 vs 2/3) before the 2nd randomization. For patients initially randomized to patisiran, there is no stratification for this 2nd randomization.

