4.4. Efficacy Evaluation

This Phase 3 study will use the APOLLO study as an external control. Patient-level data from this study will be compared with patient-level data from APOLLO for efficacy analyses.

Except for TTR endpoints, analysis models will include only the 2 treatment groups compared, vutrisiran and placebo (APOLLO), and only simple descriptives will be presented for patisiran (HELIOS-A). For TTR endpoints, vutrisiran and patisiran (HELIOS-A) will be compared unless otherwise specified.

For efficacy endpoints, 2-sided 95% confidence intervals and 2-sided nominal P values will be presented if applicable unless otherwise specified. Formal multiplicity-controlled hypothesis testing will be conducted as described in Section 1.3.1; all other P values presented will be considered descriptive.

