4.4.1.1. ANCOVA/MI

ANCOVA incorporating MI will be the default analysis for most continuous efficacy endpoints at Month 9.

MI is a broadly applicable technique for handling missing data. Missing data are imputed multiple times using a regression method. Each imputed data set is analyzed using the same analysis model, and the point estimates and standard errors are combined to provide inferences that reflect the uncertainty about the missing values. MI assumes the data are missing at random (MAR).

For a given endpoint, missing endpoint values will be multiply imputed separately for each treatment group using a regression procedure, with baseline information including baseline score and KPS as covariates and genotype, age at hATTR symptom onset, prior tetramer stabilizer use, region, FAP stage (I vs. II/III), Cardiac subpopulation, sex, and baseline NIS (<50 vs. ≥50) as factors. For NIS-related endpoints, the categorical baseline NIS score will not be included in the regression procedure.

One hundred imputed datasets (per treatment group) will be generated from the MI regression procedure using SAS PROC MI. Each of the imputed datasets will then be analyzed using an ANCOVA model, including a covariate (baseline value) and factors (treatment group; genotype; age of disease onset, baseline NIS score [<50 vs ≥ 50]), unless otherwise specified. For NIS-related endpoints, the categorical baseline NIS score will not be included in the model.

The resulting estimates (LS mean differences and standard errors) from the 100 imputed datasets will be combined using SAS PROC MIANALYZE to produce inferential results (difference in LS means, 95% CI for the difference, and the P value from the test that the difference is zero). [Rubin 1996] Combined LS mean estimates will be calculated as the average of the 100 complete-data estimates. A total variance estimate will be calculated as a weighted sum of within-imputation variance, which is the average of the complete-data variance estimates, and a between-imputation variance term. Complete details may be found in the SAS documentation for the MIANALYZE procedure (see Combining Inferences from Imputed Data Sets under Details: <http://support.sas.com/documentation/onlinedoc/stat/131/mianalyze.pdf>).

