4.4.3. Secondary Efficacy Evaluations

4.4.3.1. Key secondary endpoint: Norfolk QoL-DN Total Score

Change from baseline in Norfolk QoL-DN total score (primary analysis incorporating COVID-19 pandemic impact questions, described in Section 9.1.2) will be analyzed using an [ANCOVA/MI](#) model at Month 9, and using an [MMRM](#) at Month 18. Sensitivity, binary, and Efficacy PP Population analyses for Norfolk QoL-DN total score will also be conducted as described for mNIS+7 in Section 4.4.2.

An additional sensitivity analysis of change from baseline in Norfolk QoL-DN total score (without incorporating COVID-19 impact questions, described in Section 9.1.2) will be analyzed using an [ANCOVA/MI](#) model at Month 9, and using an [MMRM](#) at Month 18.

4.4.3.2. 10-meter Walk Test Speed, mBMI, and R-ODS

For 10-meter walk test speed (Section 9.1.4), mBMI (Section 9.1.5), and R-ODS (Section 9.1.6), change from baseline will be analyzed using an [ANCOVA/MI](#) model at Month 9 (with mBMI and R-ODS analyzed at Month 9 as exploratory endpoints), and using an [MMRM](#) at Month 18. Binary analyses for 10-meter walk test speed will also be conducted as described for mNIS+7 in Section 4.4.2.4.

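### The responder odds ratios against the external placebo group are stratified by genotype only and, unlike the plan's continuous models, have no adjustment for baseline severity (minor; descriptive analysis)

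*SAP*

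**What the plan says.** SAP Amendment 3, Section 4.4.2.4, counts "patients with a decrease (change from baseline < 0) in total score of mNIS+7 from baseline to Month 9 and to Month 18". It analyses this with a CMH test and Mantel-Haenszel odds ratios, with "associated CIs presented, stratified by genotype (V30M vs. non-V30M"). No other stratum or covariate is named.

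Section 4.4.3.1 carries the method over: "Sensitivity, binary, and Efficacy PP Population analyses for Norfolk QoL-DN total score will also be conducted as described for mNIS+7". Section 4.4.3.2 does the same for 10-MWT speed.

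The comparison is between trials. Section 4.4 states "This Phase 3 study will use the APOLLO study as an external control" and that, apart from TTR, "analysis models will include only the 2 treatment groups compared, vutrisiran and placebo (APOLLO").

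The continuous analyses adjust for more. ANCOVA/MI, MMRM and ANCOVA (4.4.1.1 to 4.4.1.3) include the continuous baseline value, genotype and age of onset, plus baseline NIS category. For one class of endpoint that category is dropped: "For NIS-related endpoints, the categorical baseline NIS score will not be included in the model". The propensity-score sensitivity analysis (4.4.2.2) adds baseline mNIS+7, Norfolk, NIS, PND, FAP, KPS, NT-proBNP and other variables, but it is applied only through ANCOVA and MMRM.

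**The concern.** Whether a patient's score falls can depend on how severe the disease was at entry. Using change from baseline does not remove that dependence, and the plan's own change-score models still include baseline as a covariate. Nothing in the design balances severity between vutrisiran and APOLLO placebo, so balance cannot be presumed.

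The reason for dropping NIS category in the continuous models does not carry over. There, a NIS-related endpoint already has its continuous baseline score in the model. The CMH analysis contains no baseline score. For Norfolk and 10-MWT it also omits NIS category, which the default model for those endpoints includes.

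At stake is how the responder odds ratio is read. It appears beside the primary analysis but lacks that analysis's protection against a difference in severity between the trials.

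**Working it through.** The SAP states no figure for the responder analysis, so there is none to reproduce. The check is an illustration.

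**Inputs from SAP Section 1.4**
- mNIS+7 change at Month 9: placebo 15 ± 17; vutrisiran mean 0.
- About 160 patients randomised 3:1, so about 160 × 3/4 = 120 on vutrisiran.

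**Assumptions, not in the SAP**
- SD 17 in both groups and within each NIS category, normal distribution.
- 60% of placebo patients with NIS ≥50; 50% or 40% of vutrisiran patients.
- Mean change worse by g = 8 or 12 points in NIS ≥50.
- 60 or 90 placebo patients.

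**Baseline rates.** Without a severity gradient, P(change < 0) is Φ(−15/17) = 0.189 for placebo and Φ(0) = 0.50 for vutrisiran, an odds ratio of 4.30.

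**Formula.** With share s of NIS ≥50 and mean m in NIS <50:

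P = (1 − s)·Φ(−m/17) + s·Φ(−(m + g)/17)

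with m = 15 − g/2 for placebo (and for vutrisiran under no effect), and m = −g/2 for vutrisiran under the planned effect.

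**No drug effect, g = 8.** The stratum probabilities are Φ(−11/17) = 0.259 and Φ(−19/17) = 0.132.
- Placebo: 0.4 × 0.259 + 0.6 × 0.132 = 0.183, odds 0.223.
- Vutrisiran, s = 0.5: 0.195; odds ratio 1.09.
- Vutrisiran, s = 0.4: 0.208; odds ratio 1.18.
- For g = 12 the odds ratios are 1.13 and 1.27.
- With NIS as a stratum the odds ratio is 1.00 throughout.
- Reversing the imbalance (s = 0.7 or 0.8 for vutrisiran, g = 8) gives 0.92 or 0.83. The bias then runs against the drug.

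**Two-sided error at nominal 5%, no drug effect** (simulated CMH test, two equal genotype strata, 120 vs 60 to 90 patients)

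| Gradient | Gap in share NIS ≥50 | Genotype only | Genotype × NIS |
|---|---|---|---|
| 8 | 10 points | 5.2–5.4% | about 5% |
| 8 | 20 points | 6.5–7.1% | about 5% |
| 12 | 10 points | 5.7–6.0% | about 5% |
| 12 | 20 points | 8.5–9.8% | about 5% |

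**Planned effect, g = 8.** The vutrisiran stratum probabilities are Φ(4/17) = 0.593 and Φ(−4/17) = 0.407, so the stratum odds ratios are 4.17 (NIS <50) and 4.52 (NIS ≥50).
- s = 0.5: vutrisiran 0.500; without NIS strata 4.48, with NIS strata 4.34; excess 4.48/4.34 − 1 = 3%.
- s = 0.4: vutrisiran 0.519; without NIS strata 4.82, with NIS strata 4.33; excess 4.82/4.33 − 1 = 11%.

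The right reference is the NIS-stratified value. The unstratified odds ratio with equal severity mix is 4.15. It falls below the stratified value because odds ratios are non-collapsible, not because of confounding.

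**The case against.** The strongest reply concerns weight. This is labelled an other analysis, appears in neither multiplicity table (Sections 1.3.1 and 1.3.2), and Section 4.4 says "all other P values presented will be considered descriptive". No efficacy claim depends on it. Severity is handled where inference is drawn: in ANCOVA/MI and MMRM, and for mNIS+7 and Norfolk also in the propensity analysis and in subgroups by NIS and FAP stage (4.4.5). Baseline NIS is tabulated by group (4.3), so a reader can see an imbalance. All of this stands and makes the point minor. It does not make the odds ratio itself unconfounded. For 10-MWT the SAP plans neither the propensity nor the subgroup analysis.

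The inputs to the illustration are also assumed. The model's placebo mean is 15.8 or 16.2 rather than the plan's 15; centring the gradient on the placebo mix changes the odds ratios by less than 1%.

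Three stronger readings are tempting, and the SAP supports none of them:
- That the responder result favours vutrisiran. The SAP gives neither the severity mix nor its relation to response, and the bias can go either way.
- That leaving out NIS breaches the randomisation. Section 3.4 says the factors "include TTR genotype (V30M vs. non-V30M) and baseline NIS score (< 50 vs. ≥ 50"), but they balance vutrisiran against patisiran, not against APOLLO placebo.
- That the trial's type I error is inflated. The 8.5 to 9.8% is the most extreme case shown, for a test outside the error-controlled family.

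**Conclusion.** The point holds as a minor improvement. The responder comparison is non-randomised, and the SAP plans no version of it that is adjusted for severity. Confounding requires both a difference in severity mix between the trials and a relation between severity and improvement; if either is absent there is none.

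Under the stated assumptions the null odds ratio moves from 1.00 to between 1.09 and 1.27. Under the planned effect with the 8-point gradient, the odds ratio exceeds the NIS-stratified one by 3% or 11%. These figures rest on assumed shares, gradient, direction and placebo sample size. The primary conclusion is not affected.

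**What to change.** In Section 4.4.2.4, do one of the following and apply it to mNIS+7, Norfolk QoL-DN and 10-MWT:
- Stratify the CMH test and Mantel-Haenszel odds ratio by genotype × baseline NIS (<50, ≥50), giving four strata.
- Use logistic regression with treatment, genotype, age at onset and continuous baseline score, adding NIS category for Norfolk and 10-MWT.

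The cost is SAP wording and one more stratification variable, or a short model statement. Every variable is already defined in the plan. The CMH option makes strata somewhat sparser, and the SAP does not give the placebo sample size needed to judge by how much. Its two-level NIS split also leaves some confounding within strata, and it omits age at onset. The logistic option avoids both limits but reports a conditional odds ratio, which differs slightly from the crude one through non-collapsibility. One sentence in the SAP should say so.
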